Given that treatment resistant MDD is a chronic disease with no known cure, management of symptoms mostly consists of trialing and failing medications whose positive effects on symptomology are of limited time course. TMS is no different. Patients that respond or remit after a TMS course will most likely see a relapse in their depressive symptoms at some point after their acute TMS treatment course is completed (3,7,8). The time course of response or remission after acute TMS treatment varies between individuals from weeks to years, and there is no way to predict the length of positive outcomes. Research has shown that close to 40% of patients will see symptom worsening, and another 10% will have a relapse within 6 months post-acute treatment course (3). Interestingly, data and clinical evidence has shown that if a patient responds to TMS and relapses back into a depressive episode, a new TMS treatment course will provide the same benefits as the original TMS course (3). In other words, if TMS works for the patient, it will most likely work again. Given the relative safety and the fact the TMS is equally effective after a positive acute response, many clinicians and researchers

have questioned the current clinical protocol of waiting for a relapse to start treating with TMS. Succinctly, should we be using TMS to maintain response?

Research using TMS as a maintenance therapy has shown that remission and response have been extended out for longer periods after the acute treatment, however there has been a multitude of parameters, populations, and treatment protocols used which has led to mixed results. These maintenance protocols studies include: as needed (10), use as a rescue (11), regular weekly or monthly intervals (10), and clustered treatments where multiple treatments are given in the same day (12).

More recently, new acute TMS protocols, called theta-burst have been FDA cleared on some TMS machines for treating depression (9). Both the original 10hz stimulation approved by the FDA in 2008, and the newer theta-burst stimulation are excitatory in nature, but little research has been completed to determine if newer theta-burst protocols are as effective and safe in maintenance of the response compared to acute TMS treatment. Further, no work has been completed on how they compare to the clinical standard 10hz during a maintenance course of treatment.

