3 minute treatment. The 37 and 20 min treatment have similar treatment protocols and total 3000 stimulations for each treatment. Both of these protocols consist of a 10Hz stimulation for 4 secs with either 27 or 11 sec intertrain break with no stimulation respectively. The 3 minute protocol is different than the other two protocols and consists of 600 stimulations per treatment. Its parameters consist of a 50Hz triplet burst stimulation for 2 seconds with a 8 second intertrain break with no stimulation.

Dosage (or % of machine output) is determined by Motor Threshold which is described in the methods section of this protocol.

This device will be used in this study because it is the current device used to treat patients for acute MDD in the UMHC Neuromodulation clinic, and the Neuromodulation clinic is where the subjects for the study will be recruited from.

This study is open-label with no sham group used as a comparative group. However, we will use a study arm that *does not* use a TMS treatment for maintenance and follow them for similar time frame as other study TMS treatment arms noting durability/length of response measures compared to other study treatment groups.

III. Recruitment Process

Subjects will be recruited from the UMHC Neuromodulation clinic. All subjects will already have completed an acute TMS treatment regime in the clinic. This study will be looking at treating in the maintenance phase only, meaning they must previously have completed the acute clinical protocol (36 treatments). Subjects will only come from the UMHC clinic, and must have responded or remitted from their depressive symptoms due to the TMS acute treatment. No participants will be allowed into the study who were acutely treated outside the UMHC Neuromodulation clinic.

As patients come close to the end of their acute clinical TMS treatment, they will be screened to see if their depressive scores have shown a clinically significant improvement, or if their symptoms have remitted (we already collect these scores clinically). If their clinical scores show this inclusion criteria then they will be approached by study staff either through face to face or by letter in mail, letting them know we have a study looking at the efficacy of using TMS treatment to maintain their improvement they have attained in their clinical course of TMS treatment.

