If a potential subject is interested in learning more about the study a copy of the consent will be given or sent to them in the mail for them to review, and a consent appointment will be setup to meet with the study staff.

IV. Consent Process

When a potential subject is identified and after a copy of the consent is given to the potential subject for review, a consent appointment will be setup. At the appointment an approved study team member will go over the privacy practices, HIPAA, and consent thoroughly, allowing the potential subject to ask questions and stressing that the signing of the consent is not a contract only a process, and that they can discontinue the study at

any time for any reason. Then if the subject is interested in starting the study the approved team member will have the subject sign and date the HIPAA and consent. Then a copy of each signed document will be given to the subject. A baseline visit will then be setup, or if time allows a baseline visit commence immediately following the signing of consent.

V. Inclusion/Exclusion Criteria

Inclusion Criteria:

[figure not shown]
- Must have recently (within 4 weeks) completed an acute TMS course (full 36 treatments) at the UMHC Neuromodulation clinic
- Must have clinically responded to the acute TMS treatment course ($\geq 50\%$ improvement according to the clinical depressive scale used - usually the PHQ-9)
- Must be able sign consent
- Must have a current address and phone number
- Must have current mental health care provider, either psychiatrist or general practitioner who they see for mental health symptom management
- Must be able to taper off antidepressant medication within 2 months of signing consent of study (treatment group only)

Exclusion Criteria:

- Subject that has not completed a full acute treatment course, including taper
- Subjects that have changed anything that may not make them safe for TMS, which are (all changes will be reviewed by study MD, and will not necessarily be excluded possibly depending on severity):
 - o Any new metal near head
 - o Any new medical devices that cannot be removed
 - o Any new pregnancies (verbally confirmed)
 - o Seizures that occurred post-acute TMS treatment
 - o Any uncontrolled cardiovascular disease
 - o Any new head trauma
 - o Any new illness causing injury to brain
 - o Any new medications which cannot be altered or lowered that may be contraindicated for TMS treatment

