 - o Any drug or alcohol use deemed by the study doctor as unsafe for TMS treatment
- Subjects unwilling to sign consent or follow study procedures
- Subjects with known extended travel plans which may affect study procedures and scheduled TMS treatment

VI. Number of Subjects

For this study we are looking to enroll 120 subjects broken down between 2 different treatment arms in the following way:

The number of subjects we expect to enroll is based on our current UMHC Neuromodulation clinic patient flow. The average patient clinic flow is 100 per year and using these numbers the study should be able to complete within 1-2 years. We expect that at least 20% of our expected enrolled may drop out of study for varies reasons (moved, loss of interest, unexpected reasons) hence the total expected completed being 100. 60 subjects in each arm will allow for a balanced study.

VII. Study Procedures/ Design/Treatment Plan

This is an open-label non-blinded study, for patients that have already completed an acute TMS course of therapy and have responded or remitted from their depressive symptoms according to their routine care clinical assessments (PHQ-9, or QIDS). There is no sham treatment in this study, but we will be using a study arm that does not receive TMS treatment in order to compare to an active TMS study arm.

All subjects will complete 3 non-treatment visits (consent, baseline, end of study visit) and if a subject is in the treatment arm and additional 60 visits (over the course of year). Additionally, a subject that is in the treatment arm will completed a PHQ-9, and IDS at baseline visit, and the beginning and end of each monthly treatment block. If a subject is in the non-treatment arm they will complete 15 total visits consisting of a consent, baseline, 12 assessment visits (for PHQ-9 & IDS testing) and an end treatment visit. For these individuals, a PHQ-9 and IDS will be completed at the baseline visit and at each monthly assessment visit.

[figure not shown]

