Subjects in the active TMS treatment arm will be tapered off their antidepressant medication as soon as they have signed consent according to the study doctor's direction. Subjects in the TMS active arm will remain antidepressant medication free for the duration of the study. If these subjects deteriorate during course of the study they will be removed from the study and normal clinical care will resume. They will complete a PHQ-9 and QIDS at this time. Their data will be used in the final analysis of study. Deterioration or relapse will be determined by the study doctor clinical judgement.

For subjects in the active TMS treatment arms, a dosing procedure (Motor Threshold) will need to be performed by any person the study PI delegates this authority to, each month immediately before the first treatment of each monthly treatment block. The Motor Threshold (MT) is used to determine the % TMS machine output or dosage, needed to treat. The procedure consists of the TMS certified operator placing the TMS machine treatment coil on the patient's head, corresponding to an area over the patients left Motor Cortex of his/her brain. Then the TMS machine intensity is turned up or down and the coil is moved around on patient's head to determined how much energy is need to elicit a muscle twitch in the right abductor pollicis brevis muscle (APB). Then a computer algorithm helps determine the correct intensity that should be used for the next 5 treatments. An additional computer algorithm uses head measurements of circumference, Nasion to Inion, and Tragus to Tragus, to determine where the TMS treatment coil will be located to treat over the Dorsolateral Prefrontal Cortex (DLPFC). This procedure must be completed each month prior to the monthly treatment block.

If a patient drops out of the study for any reason their data up to that point will be retained and used, this will be discussed with the potential patient during the consent process, and described in the consent itself.

The last treatment visit when a patient completes the treatment portion of the study or has finished their last monthly assessment visit if they are not in an active treatment arm, will be an end study visit (this could be the last treatment/assessment visit if time allows). At this visit the TMS MD will discuss end of study and possible future clinical care that maybe necessary for subject when they switch back over to clinical realm and are no longer part of the study.

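### Relapse is called by a study doctor who knows the arm, and removal at deterioration, with no later score scheduled, is written for the TMS arm only, so length of response may not be measured alike in both arms

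*Protocol*

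**What the plan says.** Section II (Drugs/Biologics/Devices) sets the comparison. The study will take a no-TMS arm and "follow them for similar time frame as other study TMS treatment arms noting durability/length of response measures", compared with the treated group. Section VII states that "This is an open-label non-blinded study".

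The paragraph of Section VII on the active arm says that its subjects are tapered off antidepressants and stay off them. If these subjects deteriorate, they leave the study, return to normal care and complete a PHQ-9 and QIDS at that time, and their data enter the final analysis. The paragraph ends: "Deterioration or relapse will be determined by the study doctor clinical judgement". No score threshold is given. Section VII also says that for anyone who drops out, data up to that point are kept and used.

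For the no-TMS arm, Section VII says that "a PHQ-9 and IDS will be completed at the baseline visit and at each monthly assessment visit", with 12 such visits. The active arm is scored before and after each of its 12 monthly blocks.

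Section V does contain a score-based response criterion for entry: at least 50% "improvement according to the clinical depressive scale used - usually the PHQ-9". Section I separates worsening from relapse: "close to 40% of patients will see symptom worsening, and another 10% will have a relapse within 6 months post-acute treatment course".

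**The concern.** Length of response depends on when response is declared lost. Two routes to that date are open, and neither is set up equally in the two arms.

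- **The doctor's call.** The doctor knows the arm, and the text draws no line between worsening and relapse, although Section I treats them as different things with very different frequencies. The call could be made earlier or later in one arm, in either direction.
- **The scores.** Both arms are scored monthly, but a TMS subject judged to have deteriorated is removed, and no later score is scheduled. If the removal score has not crossed whatever threshold the analysis uses, the later course is unknown. No matching step is written for the no-TMS arm, apart from the study doctor's general power over participation in Section VIII.

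An analysis plan can define relapse from scores. It cannot recover scores that were never taken, nor extend a consent that describes keeping data only up to drop-out.

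**Working it through.** The protocol gives no relapse rate, alpha or power for this comparison, so there is no stated figure to reproduce. The check sets out what each arm yields and then shows how large the distortion could be under stated assumptions.

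**Schedule (Section VII)**

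| | TMS arm | No-TMS arm |
|---|---|---|
| Scorings over a full course | 1 + 2×12 = 25 | 1 + 12 = 13 |
| Written step at deterioration | Removal, one PHQ-9 and QIDS | None in the available text |
| Scores scheduled after that step | None | Monthly visits continue |

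**A. Score-based relapse, early removals censored.** Assumptions: 60 per arm (Section VI), no true effect, a constant monthly hazard, a true 12-month relapse p of 30% to 50%, and a share q of TMS-arm relapsers removed before the score event. The removed subjects are those about to relapse, so the TMS-arm estimate becomes 1 − (1 − p)^(1 − q).

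- p = 0.30, q = 0.10: 1 − 0.70^0.90 = 0.275, which is 2.5 points too low.
- p = 0.50, q = 0.30: 1 − 0.50^0.70 = 0.384, which is 11.6 points too low.

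Simulated rejection rates of a nominal two-sided 5% log-rank test (4,000 or more trials per setting), for p from 0.30 to 0.50:

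| q | Rejection rate |
|---|---|
| 0 | about 5% |
| 0.05 | about 5% to 6% |
| 0.10 | about 6% to 7% |
| 0.30 | about 15% to 24% |

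**B. Censoring against counting removal as relapse.** A second simulation gave both arms the same latent PHQ-9 course, with relapse at PHQ-9 of 10 or more (all parameters assumed). Relapse at 12 months in the no-TMS arm is about 0.50. With a monthly chance of removal for sub-threshold worsening of 0.1, 0.5 and 1, the TMS arm shows:

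- 0.46, 0.37 and 0.32 if removals are censored;
- 0.53, 0.58 and 0.61 if removals count as relapse.

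The error changes sign with the handling. Using both monthly scores in the TMS arm, with no removals, gives about 0.55 against 0.50, simply because that arm is looked at twice as often.

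**C. The doctor's call as endpoint.** This applies only if the analysis uses it. If a share u of relapses is missed in one arm, the rates are p and p(1 − u). Exact enumeration of the pooled two-proportion test, 60 per arm:

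- 0.30 v 0.27 (u = 0.1): rejects in 6.8%
- 0.40 v 0.32 (u = 0.2): 14.9%
- 0.50 v 0.35 (u = 0.3): 39.2%

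Equal rates give 5.1% to 5.5%.

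Section I's 6-month figures show the room for judgement. Calling relapse only gives 10%, and calling any worsening gives 10% + 40% = 50%, or 6 to 30 of 60 subjects. They come from a cited study whose definitions are not shown, so they illustrate the spread and do not bound it.

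**The case against.** The strongest case against has five parts.

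1. *The sentence on clinical judgement closes a paragraph about active-arm removal, so it may only say who decides removal. Endpoint definitions belong in an analysis plan.* This stands in part. The protocol never says that the judged call is the endpoint, so part C is conditional, and the lack of a relapse definition is not itself the finding. The collection of scores after removal and the consent are protocol matters, however, and an analysis plan cannot supply them.
2. *A score is taken at removal, and those data are to be analysed.* This stands and narrows the point. For time to first loss of response, nothing is lost if the removal score has already crossed the threshold. But nothing ties removal to a score, so that cannot be assumed.
3. *The magnitudes are assumed.* This stands. The low ends are close to nominal. With 20% dropout (60 × 0.8 = 48 per arm), the 39% in part C falls to 32%.
4. *One-arm removal follows from one-arm tapering.* True, and the passages do not contradict each other here. The taper explains the step but does not make the measurement equal.
5. *The PHQ-9 is completed by subjects who know their arm.* True. A score rule removes the doctor's discretion, not open-label bias.

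A reader might infer that the design favours TMS. The documents do not support that: censoring early removals favours TMS, counting them as relapse can do the opposite, and the judged call can err either way. Nor do they support inferring that every removed subject is lost to a score-based analysis, or that the no-TMS arm certainly has no deterioration step. A figure in Section VII is missing from the available text, and Section VIII gives the doctor general discretion.

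**Conclusion.** The point holds in a limited form and should be fixed. The only relapse criterion written is an unblinded judgement. In the available text, removal without later scoring is written for the TMS arm alone, although length of response is what the arms are compared on. A judged analysis is exposed to that judgement, and a score-based one to gaps in one arm.

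The size depends on how many TMS subjects are removed before crossing the score threshold, which the documents do not give. Under the assumptions of part A, the effect is negligible to small up to 10% of relapsers and material at 30%. The net direction cannot be stated.

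**What to change.** Leave the study doctor's judgement in place for care. For the analysis:

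- Define loss of response identically in both arms from the PHQ-9, anchored to the protocol's own criterion of at least 50% improvement from the score before the acute course. That earlier score is not in the study schedule. Section III says the clinic collects such scores, so state that it will be retrieved, and set a PHQ-9 rule for subjects who qualified on another scale.
- Have the sponsor set any margin or confirmation rule in advance. Some protection is needed: a stable subject who enters at exactly 50% improvement can cross the line through score noise alone.
- Use the pre-block PHQ-9 as the TMS arm's monthly value, matched to the no-TMS monthly visit.
- Continue the monthly PHQ-9 to month 12 by phone or mail in both arms after any removal for deterioration, with matching consent wording. Section V already requires this: "Must have a current address and phone number".
- Record in both arms the date of any return to clinical care or change of depression treatment, and apply one prespecified counting rule to both.
- Report the result both with such events counted as relapse and from scores only. The first relies on the unblinded call, and the second includes scores taken under resumed care.
- State as a limit that subjects complete the PHQ-9 knowing their arm.

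The sponsor should also reconcile between the arms what happens at deterioration. No clinical rule is proposed here.

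Cost: protocol wording and a consent amendment, with no new assessor or instrument. If 30% to 50% of 60 TMS subjects are removed, on average at mid-year (assumed), the added forms number 60 × 0.3 × 6 = 108 to 60 × 0.5 × 6 = 180. A confirmation rule, if chosen, would delay the relapse date by up to one month.

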Study procedure plan is below:

Study visit completion for TMS active arms form is below, subjects that are in non-active arm will not have the TMS treatment visits, but will do the monthly assessment visits:

Visit	Consent	Hipaa	Inclusion/Exclusion	TASS	PHQ-9*	QIDS*	AE **
Consent	x	x					
Baseline			x	x	x	x	
Trt 1-5 (1 Month)					x	x	
Trt 6-10 (2 Month)					x	x	
Trt 11-15 (3 Month)					x	x	
Trt 16-20 (4 Month)					x	x	
Trt 21-25 (5 Month)					x	x	
Trt 26-30 (6 Month)					x	x	
Trt 31-35 (7 Month)					x	x	
Trt 36-40 (8 Month)					x	x	
Trt 41-45 (9 Month)					x	x	
Trt 46-50 (10 Month)					x	x	
Trt 51-55 (11 Month)					x	x	
Trt 56-60 (12 Month)					x	x	

* Completed before and after each monthly TMS treatment block

** Adverse Event form to be filled out as needed

VIII. Potential Risks/Adverse Events

The machine and treatment protocols are the same used in the clinical setting, therefore the risks are the same. The most common side effect/ risk is headache, superficial pain under treatment site, dental pain, eye pain, or facial muscle twitching. These seem to well tolerated, and can occur during or after treatment. These can be treated with over-the-counter pain medication (Tylenol, Ibuprophen).

Another rare but serious risk is seizure. Seizures are very rare and are thought to occur about 1 in 30,000 treatments. Subjects will have already gone through safety screens in order to get TMS treatment clinically, but nevertheless, another Transcranial Adult Safety Screen (TASS) will be done prior to starting treatment phase of study. Study staff are trained in seizure occurrence during TMS and are also CPR certified.

The study doctor will determine if patient participation should start or continue from these or any other subject problems that may occur, such as failure of TASS question throughout the study.

If an adverse event, UP, or deviation occur study staff will fill out a study adverse event form, the AE event log, and will notify the MU IRB if required within 5 days of awareness of the event.

IX. Anticipated Benefits

It is not known whether TMS used in a monthly maintenance protocol will be beneficial in helping to extend out the subject's acute response or remission, but it may be a possible benefit. Additionally, this study will help add to the work of clinical and scientific community in this area of interest. This data may also help future patients that have MDD and are trying to maintain their response.

X. Compensation

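### Apart from one exit score on deterioration, active-arm depression scores are scheduled only around TMS blocks, so a missed block or a stop for another reason leaves months with no score

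*Protocol*

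**What the plan says.** Protocol Section VII schedules active-arm scoring "at baseline visit, and the beginning and end of each monthly treatment block". The footnote to the visit table in that section repeats this: "Completed before and after each monthly TMS treatment block". The rows of the table are numbered by treatment, five per month, so an active-arm month is in effect a block number. The three non-treatment visits common to all subjects are consent, baseline and end of study. The active arm therefore has no stand-alone monthly assessment, and no score is assigned to the end visit.

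The no-TMS arm is described differently. Its 15 visits include "12 assessment visits (for PHQ-9 & IDS testing) and an end treatment visit", with scores taken at baseline and at each monthly assessment. The lead-in to the visit table says that "subjects that are in non-active arm will not have the TMS treatment visits, but will do the monthly assessment visits".

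Two further rules in Section VII matter. An active-arm subject who deteriorates is removed from the study, completes a PHQ-9 and QIDS at that time, and stays in the final analysis. Any subject who drops out, in either arm, contributes data up to that point. Section VIII adds that "The study doctor will determine if patient participation should start or continue from these or any other subject problems that may occur", which covers side effects and failed safety-screen questions.

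**The concern.** Section II sets out a comparison of durability or length of response between the arms over a similar time frame. In one arm measurement depends on receiving the intervention; in the other it does not. If an active-arm subject skips a block, nothing is scheduled that month. If TMS stops because of a side effect, a safety-screen problem or the burden of 60 treatment visits, scoring stops with it, and a later loss of response is never recorded against the maintenance strategy. If a block is late, its score is taken at a different calendar time from the no-TMS score carrying the same month label.

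Skipping or stopping may well be related to how the subject is doing, in which case the missing scores are not a random subset. This is a question of data collection, so no analysis plan can recover scores that were never scheduled.

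**Working it through.** **Visit counts.** No-TMS arm: 1 consent + 1 baseline + 12 assessments + 1 end visit = 15, as stated. Active arm: 12 blocks × 5 treatments = 60, as stated.

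**Scoring occasions with full adherence.** Active: 1 + 2 × 12 = 25. No-TMS: 1 + 12 = 13. With full adherence the active arm is scored every month and there is no gap.

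**One subject who stops TMS.** After block *m* there are 1 + 2*m* scores and 12 − *m* months without one. For *m* = 3, 6 and 9 this gives 7, 13 and 19 scores, then 9, 6 and 3 unscored months. One exit score is added only if the reason is deterioration.

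**The arm of 60 (Section VI).** Assume stops spread evenly after blocks 1 to 11, a mean of 6 months lost. If 20% stop, that is 12 subjects, 12 × 6 = 72 of 60 × 12 = 720 subject-months (10%), and month-12 status unknown for 12 of 60. For 10% to 50% stopping, 5% to 25% of subject-months are unscored and month-12 status is unknown for 6 to 30 of 60. Separately, each 10% of blocks missed outright leaves at most 0.10 × 720 = 72 months without a score.

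**Effect on the 12-month maintained share.** Inputs:
- Six-month loss share *p* without TMS, from Section I: close to 40% worsening plus another 10% relapse. Use *p* = 50% (both pooled) or *p* = 10% (relapse alone).
- Assumed: a constant loss rate, halved while on TMS and returning to the off-TMS rate after stopping; a share *q* stopping for reasons other than deterioration; stop times uniform over 12 months and unrelated to prognosis.

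The off-TMS monthly rate is *r* = −ln(1 − *p*)/6, which is 0.1155 or 0.0176. At half that rate, the share maintained over 12 months on TMS is G = exp(−6*r*) = 1 − *p*. Among stoppers, the share still in response at stopping is L = (1 − G)/(−ln G), and the share truly in response at month 12 is G × L. Hence:
- True share = (1 − *q*)G + *q*GL
- Last-score share = (1 − *q*)G + *q*L
- Share with censoring at the stop = G

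With *q* = 20%:

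| | *p* = 50% | *p* = 10% |
|---|---|---|
| G | 0.500 | 0.900 |
| L | 0.5/0.693 = 0.721 | 0.1/0.1054 = 0.949 |
| GL | 0.361 | 0.854 |
| True | 0.8 × 0.500 + 0.2 × 0.361 = 0.472 | 0.8 × 0.900 + 0.2 × 0.854 = 0.891 |
| Last score | 0.8 × 0.500 + 0.2 × 0.721 = 0.544 | 0.8 × 0.900 + 0.2 × 0.949 = 0.910 |
| Censored | 0.500 | 0.900 |
| Excess, last score | 7.2 points | 1.9 points |
| Excess, censored | 2.8 points | 0.9 points |

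Losses after stopping that go unseen: 12 × (0.721 − 0.361) = 4.3 of 60 at *p* = 50%, and 12 × (0.949 − 0.854) = 1.1 of 60 at *p* = 10%.

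The excess is proportional to *q*. For *q* from 10% to 30%, the last-score excess at *p* = 50% runs from 3.6 to 10.8 points, and the censored excess at *p* = 10% from about 0.5 to 1.4 points.

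**The case against.** A reader might infer that the active arm is observed only while on treatment and the no-TMS arm completely for 12 months. The documents support neither half. Section VII gives deteriorating active-arm subjects an exit PHQ-9 and QIDS and keeps their data, so that event is captured. The dropout rule applies to every subject, and the dropout of at least 20% expected in Section VI is not specific to one arm, so the no-TMS arm will have gaps too.

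The affected group is also an inference. The protocol describes no status of being off TMS but still enrolled. The Section VIII sentence concerns participation, not stopping TMS while staying in. The Section VI reasons for dropout, such as moving or losing interest, are largely departures that continued scoring may not recover. Section V already excludes known extended travel, and a delayed block is still scored, so the missed-block figure is a ceiling.

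The size is soft. The protocol states no last-score analysis, and the handling of missing data may lie in an analysis plan that is not shown. Pooling worsening with relapse gives the upper end. With 60 subjects the standard error of a 50% share is √(0.25/60), or 6.5 points, so the lower figures are small beside sampling error. The model also takes stopping as unrelated to prognosis, so it does not measure any informative missingness. Finally, censoring at the stop can be a legitimate target if the question is what happens while TMS continues.

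All of this limits the size and the wording. It does not remove the difference in scheduling. A protocol followed exactly still produces no score in these months, and an analysis that wanted the outcome of the whole strategy would have nothing to use.

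**Conclusion.** The point holds in limited form. Apart from the exit score on deterioration, every scheduled post-baseline active-arm score depends on a TMS block, whereas the no-TMS monthly assessments do not depend on treatment. The months exposed are those with a missed block and those after a stop for a reason other than deterioration; delayed blocks add a shift in timing.

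The documents do not give the size, because they do not say how many subjects will skip or stop TMS and could still be scored. With an assumed 20% stopping and a halved loss rate on TMS, the 12-month maintained share is overstated by about 1 to 7 points: 1 to 2 points if the Section I loss is 10% by six months, and 3 to 7 points if it is 50%, with censoring at the low end of each pair and last score at the high end. An overstatement of up to 11 points needs 30% stopping, the pooled loss rate and a last-score analysis together, and the protocol commits to none of these. The change is still worth making, because it is cheap and the missing scores cannot be recovered later.

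**What to change.** Amend Section VII and the visit-table footnote as follows:

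- Schedule the PHQ-9 and the second scale monthly in both arms, dated from baseline (months 1 to 12) and due whether or not a block is given. Where there is a block, take the score before it.
- Continue the same monthly assessments for active-arm subjects who miss a block, or who stop TMS without withdrawing consent.
- Compare the arms on these dated monthly scores and keep the other block scores as additional data.
- Describe scoring after TMS stops as assessment follow-up only. Reconcile it with the Section VII statements on removal from the study on deterioration and on remaining free of antidepressants for the duration of the study, without changing any treatment rule.

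The cost is a protocol amendment and one questionnaire contact for each month without a block. The instruments and the 12-visit schedule already exist. The active-arm figure may come out somewhat less favourable.
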